1.0 Objectives / Specific Aims

Aim 1: Modify Alcohol and Sexual Assault Prevention (ASAP) content to an eHealth format to include personalized content for each risk group (1. cisgender heterosexual men; 2. cisgender heterosexual women; and 3. sexual and gender minorities).

Aim 1a: Assess normative behaviors ($n = 750$) regarding alcohol use and SA for feedback from Arizona State University (already completed and de-identified data being analyzed) and Georgia State University.

Aim 1b: Adapt and assess initial acceptability of a workbook version of the intervention content among key stakeholders (college administrators and students from each risk group [$n=5$ from each group]) from Arizona State University (already completed and de-identified data being analyzed) and Georgia State University.

Aim 2: Open Pilot Trial. Obtain usability of ASAP among 30 students who engage in HED (10 from each risk group) in an open pilot trial at Arizona State University (already completed and de-identified data being analyzed) and Georgia State University.

Aim 3: A pilot to assess effect size and variability for planning a randomized trial in the future. This Aim will only be conducted at Arizona State University. Randomize students who engage in HED to ASAP or control condition to observe preliminary effect sizes and estimate the variability using a 3-month follow-up. Sample size was determined to estimate the variability within a reasonable margin of error. This calculation also accounted the low base rates of SA and 20% attrition. This led to a sample size of 162 students ($n=54$ from each risk group).

By accomplishing these aims, we will have established the research team, programming, feasibility and preliminary efficacy of the research protocol. If promising, this study will lay the groundwork for an R01 application to test the efficacy of ASAP.

2.0 Background

This study aims to conduct a pilot of a behavioral intervention for heavy episodic drinking (HED) and sexual assault (SA) among college students. Approximately 20% of women experience SA during college with the highest rates of victimization among women and sexual/gender minorities. SA results in significant public health costs with US government sources paying an estimated \$1 trillion of the total \$3.1 trillion of lifetime costs accrued by SA. The federal guidelines and the Center for Disease Control (CDC) recommend that colleges provide universal SA prevention that incorporates bystander intervention and victimization risk reduction strategies. Although bystander intervention is evidence-based and engages all members of a campus in violence prevention, bystander intervention fails to address the gender-specific factors associated SA victimization and perpetration risk, and fails to address the pervasive role of alcohol in SA. Further, many universities use commercially available mHealth (mobile health) products that currently show no documented efficacy in reducing SA to address this public health concern rather than evidence-based prevention programming. A new approach is needed that can appeal to university administrators nationwide and includes evidence-based bystander and risk reduction content personalized by risk factors, including gender, sexual minority status, and alcohol use. Alcohol is involved in half of SA among college students. SA prevention that does not directly target HED is ineffective for college students who engage in HED. This is problematic because 40% of college students engage in HED, and students who engage in HED are at highest risk of SA victimization and perpetration. It is imperative to develop and test SA interventions aligned with best practices in prevention to provide bystander intervention training, that targets the role of alcohol in SA (and therefore appropriate for students who engage in HED), and provides information relevant to risk and protective factors for SA. Personalized approaches to SA intervention recognize that risk and protective factors for SA vary among

men, women, sexual minorities, and gender minorities; requiring that intervention be personalized in content and approach.

Our research team has developed and tested two gender-specific programs that integrate alcohol and SA intervention for college students. [name] (PI) evaluated the efficacy of a web-based combined alcohol use and SA risk reduction program for college women who engaged in HED. It was most effective over a 3-month follow-up at reducing HED and victimization among women with more severe SA histories and was featured in the NIAAA Director's Report on Institute Activities to the 141st Meeting of the National Advisory Council on Alcohol Abuse and Alcoholism¹⁵. This intervention focused on reducing SA victimization dovetails an integrated alcohol and SA intervention developed and tested by the research team (R34 AA020852), designed to reduce perpetration of SA among college men. Preliminary findings suggest that the in-person approach, is feasible, acceptable and promising to reduce SA perpetration and facilitate proactive bystander intervention among college men. These preliminary studies suggest that a mHealth SA prevention approach for women and men that includes bystander intervention and incorporates theory-driven intervention to reduce risk of SA victimization and perpetration is a promising next step. Given that prior work by the research team lacked a focus on the applicability of integrated alcohol and SA prevention programs for gender and sexual minorities, work is also needed to ensure that an integrated alcohol and SA prevention program is appropriate, acceptable, and useful for all members of a campus community. Accordingly, the present research will develop a new multi-pronged, personalized mHealth application targeting alcohol and SA that incorporates the research team's previous work, and infuses standardized bystander intervention content into the approach while also including content on sexual and gender minorities. Our developmental work will ensure that this intervention can be disseminated nationwide with minimal tailoring and cost, thereby addressing the research-practice gap in college SA prevention.

3.0 Intervention to be studied

Intervention Descriptions

Below is a description of each of the intervention components to be integrated into personalized feedback based on gender identity and sexual minority status as described above. While concurrently adapting in person interventions to mHealth interventions (bystander and SA perpetration prevention components as described below) as well as developing sexual and gender minority content, college-specific normative behavior will be collected to integrate into intervention content.

HED feedback component (all risk groups): HED content will be included in the ASAP interventions and has already been developed and used in mHealth delivery modes. Alcohol is directly targeted using algorithm- driven personalized feedback and a social norms approach using web-based BASICS (Brief Alcohol Screening and Intervention for College Students; BASICS) with integrated SA information. A recent meta-analysis assessing the effects of BASICS indicated significant reductions in alcohol use and alcohol-related problems. Web-based BASICS provides the same content in BASICS but online. It provides feedback regarding drinking behavior and consequences. Drinking is compared to perceived and actual gender-specific drinking norms to correct misperceptions regarding normative drinking behavior. Personalized interactive education regarding definitions of a standard drink, gender differences in blood alcohol content, alcohol expectancies and alcohol myopia, and personalized gender-specific information about risks associated with blood alcohol content is provided. Integrated into these alcohol components include examples of SA (i.e., when presenting information about alcohol's cognitive impairment effects the example of decreases in SA risk perception are provided). For transgender students, biologically-based feedback (i.e., blood alcohol content charts) will be provided based on biological sex and normative feedback will be provided based on identified gender.

Adaptation for current study: No adaptation is except for incorporating Arizona State University (ASU)-specific norms and pictures into the mHealth application.

SA risk reduction component (all risk groups): The SA risk reduction content is an already developed web-based intervention, therefore adapting to an mHealth format only includes small changes to the content. This component was originally developed for primarily cisgender heterosexual women. This intervention is rooted in a feminist framework that places the blame on SA perpetrators but provides theoretically-based risk reduction programming (Cognitive Mediational Model and Assess, Acknowledge, and Act). Risk reduction programming targeting these theoretical constructs is relatively new and has yielded significant decreases in SA victimization and has demonstrated efficacy for up to a 2-year follow-up period. The core educational components on SA components include psychoeducation about SA prevalence in the setting (at the specific college), state laws, and college guidelines about what constitutes a SA. In the survey immediately preceding the intervention, participants are presented with a hypothetical SA scenario and they indicate when they would leave the scenario and what resistance strategy they would likely choose. Feedback is given on the strategy choice and other potential strategies are given. Further, barriers to resistance are discussed including social relationships with the perpetrator, use of alcohol, and fear of making the situation worse, and individuals are provided with potential ways to combat the barriers. Information regarding the association between alcohol use and SA is also provided.

Support for this approach: We conducted a RCT evaluating a web-based normative comparison personalized feedback intervention to reduce HED and SA for undergraduate college women who engaged in HED (AA020134; PI: [name]) that was developed by [name] (PI). College women ($n = 264$) were randomly assigned to: 1) alcohol personalized feedback intervention, 2) SA personalized feedback intervention, 3) combined alcohol and SA personalized feedback intervention, 4) assessment only control, 5) minimal assessment control. Retention rates were 78.41% at 3 months. The combined personalized feedback intervention was the only personalized feedback intervention successful at reducing alcohol-involved SA frequency. There was a significant interaction between SA history severity and the combined condition on SA severity, HED, and frequency of incapacitated rape at follow-up such that the combined intervention was more effective at reducing these outcomes for individuals with more severe SA histories at baseline. A secondary outcome analysis revealed that the combined alcohol and SA personalized feedback intervention, compared to the assessment only control conditions, was associated with less drinking to cope with anxiety symptoms at the three-month follow-up for women with higher drinking to cope with anxiety motives. Further, drinking to cope with anxiety symptoms mediated the effects of the combined intervention on heavy episodic drinking outcomes. Taken together, this suggests strong preliminary findings of this intervention component for college women who engage in HED.

Adaptation for current study: For cisgender heterosexual women, no adaptation is needed except for incorporating ASU-specific norms and pictures. For cisgender heterosexual men, education regarding SA rates among men and brief general risk perception information (specific information about SA risk perception and risk factors among men as victims is not yet well established). For sexual and gender minorities, specific risks including being targeted for SA victimization and rates of SA among gender and sexual minorities will be included. Acquiring university-specific data on SA is beyond the scope of the current study, therefore, feedback will be based on previous national studies, including those conducted by the research team ([name]; consultant). Examples of potential SA situations will include a broad range of victim-perpetrator relationships to best capture the experiences in this risk group. Further, due to the role of minority stress on mental health outcomes after experiencing SA among sexual and gender minority populations, education regarding this association will be included in the content.

SA perpetration prevention component (cisgender heterosexual men): The SA perpetration prevention content is already developed for in person delivery modes and will be included only in the men-specific ASAP intervention. This content will be adapted for a mHealth application from the discussion-based module of the Men's Workshop. This intervention includes feedback regarding one's own fear of false accusations and education regarding actual false accusation rates. Perceived rates of SA perpetration are compared to actual university-specific rates. Misperception of college men's sexual behavior including frequency of sex and number of sexual partners are corrected using personalized normative feedback to relieve men of the social pressure they may feel to have sex. Education regarding sexual consent which includes example scenarios is provided. All of this content is easily translatable to mHealth a delivery mode.

Support for this approach: The SAFE program is grounded in the Men's Workshop, a SA prevention model that, in preliminary work funded by the Centers for Disease Control and Prevention (CDC), showed 50% reductions in SA perpetration among college men over four months. Specifically, four months after the program, 1.5% of men in the treatment group reported sexual aggression compared to 7% of men in the control group ($p < .05$). Next, through NIAAA-funded projects (R34AA020852; PI: [name]), (R34 AA020852), [name] integrated a brief motivational interviewing personalized feedback protocol (similar to that described in the HED component above) in conjunction with the Men's Workshop. Initial findings of 25 college men who engage in HED indicated that SAFE is a feasible, acceptable and useful approach. Specifically, participants rated the intervention as high quality ($M=3.8$, $SD = 0.48$, Scale 0-4), were satisfied with the program ($M=3.7$, $SD=0.46$, Scale 0-4), and indicated that they would participate in the program again ($M=3.4$, $SD=0.58$, Scale 0-4). Findings of a randomized pilot trial also revealed promising effects over a 2- and 6-month interim among SAFE participants, in comparison to a dose- and attention matched control.

Adaptation for current study: The in-person manual written by [name] will be adapted to an mHealth delivery format using the following procedures that are built into the study aims: initial adaptation completed by the investigative team, alpha testing (Aim 1) with end users and beta (Aim 2) testing with end users prior to finalization. The content is revised to incorporate feedback from end users at all stages of the adaptation. The investigative team have successfully used this strategy for mHealth applications (EMW-2015- FP-00759; PI: [name]; Co-I: [name]; 2016-RF-GX-001; PIs: [name]/[name]; Technology Coordinator: [name]). A brief education only version of the content will be developed for women and sexual/gender minorities as well because populations other than cisgender heterosexual men can also be SA perpetrators.

Bystander intervention component (all risk groups): Bystander intervention content is already developed for in person delivery modes and will be included in both the women- and men-specific ASAP interventions. The bystander intervention approach focuses on targeting SA perpetration by eliciting bystanders to intervene in potential SA situations and target social norms for SA. This content will be adapted to a mHealth delivery mode from the discussion-based module of the Men's Workshop. This module includes university- specific feedback regarding perceived and actual social norms of men engaging in insensitive behavior towards women (i.e., using the word "slut" to insult a woman or men joking about having sex with a woman), psychoeducation regarding barriers to intervening with potential SA situations, and practice scenarios using effective intervention strategies, all of which are easily translatable to mHealth delivery modes.

Support for this approach: Bystander intervention as incorporated with the Men's Program has been studied by [name] as described above.

Adaptation for current study: The adaptation strategy will be the same as the perpetration prevention content described above.

Control Group: The control group will be compared to those assigned to the intervention (intervention components described above. The control group will be an assessment only control, meaning that they will only complete the assessment at baseline instead of receiving an intervention.

4.0 Study Endpoints

Outcome variables include alcohol use, bystander behavior, and sexual assault victimization 3-months after the intervention. Further, self-blame will be assessed directly after receiving the intervention to ensure that the intervention does not have iatrogenic effects (even though previous iterations of this intervention have found no iatrogenic effects).

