Aim 3: Upon agreeing to participate in the study, participants will be automatically re-directed to complete a 30-minute online survey regarding their demographics, alcohol use, sexual assault experiences, and bystander experiences and attitudes (Aim 3 Baseline Survey). Upon completing the survey, they will be randomly assigned to either receive the personalized feedback intervention (described above) or to an assessment only control condition. If they were assigned to receive the personalized feedback intervention, they will be automatically directed to receive the personalized feedback intervention (described above). This intervention will take approximately 15 minutes to complete. Immediately following the intervention, they will complete a 15-minute post-intervention survey regarding their feedback and immediate potential outcomes (post-intervention survey). A total of 162 eligible participants will be paid \$25 for completing the baseline portion of the study. Upon completing the post-intervention survey, they will be given local resources regarding alcohol use, sexual assault, and mental health resources (see Resources). All participants will be given this information, regardless of their risk. Participants will be given the option of contacting the study staff if they are distressed by the study procedures. Members of the research team are licensed clinical psychologists and are well-equipped to follow-up with individuals in need. As been the case with our previous studies, we will establish a schedule in which members of the research team will be on call 24 hours a day, seven days a week to address urgent matters. If a participant is distressed and wishes to talk with a member of the research team, the clinical psychologist team member will be available at all times during the study period. The procedure will be the same for Arizona State University student and administrator participants except student participants will be compensated for their time and administrators will be volunteering their time.

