Participants will be contacted 3 months after completing the initial survey in an email (Aim 3 Follow-Up Email) with their PIN. The follow-up survey will be exactly the same as the baseline survey, except time periods will include the “past 3 months” for questions. Participants will have one month to complete the survey and will be sent reminder emails if they have not completed the survey. Upon completing the survey, they will be emailed an e-gift card for \$35 for completing the survey. Upon completing the survey, they will be given local resources regarding alcohol use, sexual assault, and mental health resources (see Resources). All participants will be given this information, regardless of their risk. Participants will be given the option of contacting the study staff if they are distressed by the study procedures. Members of the research team are licensed clinical psychologists and are well-equipped to follow-up with individuals in need. As been the case with our previous studies, we will establish a schedule in which members of the research team will be on call 24 hours a day, seven days a week to address urgent matters. If a participant is distressed and wishes to talk with a member of the research team, the clinical psychologist team member will be available at all times during the study period. The procedure will be the same for Arizona State University student and administrator participants except student participants will be compensated for their time and administrators will be volunteering their time.

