12.0 Data Management

The research material obtained from human participants in this protocol will include:

1. De-identified survey questionnaire to obtain normative attitudes and behavior related to alcohol use and sexual assault;
2. De-identified survey and open ended questions assessing the usability of the interventions within an open pilot trial;
3. De-identified survey and open ended questions assessing the usability of the interventions within a randomized pilot trial and follow-up alcohol use and sexual assault-related constructs 3 months after receipt of intervention (if assigned to ASAP condition) or completion of baseline survey (if in control condition).

Recruitment Sources/Sites Where Data Will Be Collected and How These Data Will Be Obtained, Managed, and Protected:

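### As described, self-blame is scored only in the ASAP arm, with no documented baseline score and no named analysis, so it cannot support a conclusion of no iatrogenic effects

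*Protocol*

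**What the plan says.** Protocol section 4.0 gives self-blame a harm purpose: "self-blame will be assessed directly after receiving the intervention to ensure that the intervention does not have iatrogenic effects". It adds in parentheses "even though previous iterations of this intervention have found no iatrogenic effects".

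Four other places determine what data that check would produce.

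- **Control arm.** Section 3.0, Control Group: "The control group will be an assessment only control, meaning that they will only complete the assessment at baseline instead of receiving an intervention".
- **Aim 3 procedure.** Section 10.0: "If they were assigned to receive the personalized feedback intervention, they will be automatically directed to receive the personalized feedback intervention". After the duration is given, the text continues: "Immediately following the intervention, they will complete a 15-minute post-intervention survey regarding their feedback and immediate potential outcomes". The baseline topics listed there are demographics, drinking, experience of sexual assault (SA), and bystander matters. Self-blame is not named.
- **Follow-up.** Section 12.0 times the follow-up data at "3 months after receipt of intervention (if assigned to ASAP condition) or completion of baseline survey (if in control condition"). Section 10.0 says "The follow-up survey will be exactly the same as the baseline survey", apart from the recall period.
- **Analysis.** The SAP (Sample Size and Analyses) plans secondary linear mixed model ANOVAs. Its examples of outcomes are alcohol use, SA victimization and bystander intervention. It gives no contrast, interval or rule for self-blame.

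**The concern.** A score taken once, after the intervention, in treated participants only, gives neither a within-person change nor a randomised difference. A high mean could reflect the sample's assault history, and a low mean could hide an increase caused by ASAP. Neither can be attributed to the programme, yet section 4.0 gives this measure the task of establishing that the programme does no such harm.

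The reassurance from previous iterations carries over only in part. Section 3.0 says that the SA risk reduction component was built mainly for cisgender heterosexual women. The content for men and for sexual and gender minorities is added in this study. Section 2.0 says that the team's prior work lacked a focus on those minorities. By design, two of the three risk groups (2 × 54 = 108 of 162) lie outside the population for which that component was mainly developed. The pilot is meant to support a larger grant application, so an unsupported statement of no harm could be carried into it.

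**Working it through.** The documents state no figure, scale or SD for self-blame, so there is no planned number to reproduce. The check has two parts.

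**1. Which scores exist under the plan as described**

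| Time | ASAP arm | Control arm |
|---|---|---|
| Baseline survey | self-blame not named | self-blame not named |
| Directly after intervention or randomisation | self-blame scored (section 4.0) | no survey described |
| 3 months | same items as baseline | same items as baseline |

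The 3-month survey repeats the baseline survey. A self-blame comparison at 3 months therefore exists only if the items are already in the baseline survey. On the text alone, the only documented self-blame score is in one cell of this table.

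With 162 randomised and 1:1 allocation (assumed, as the ratio is not stated), that cell holds 162/2 = 81 scores. The mean would have a 95% half-width of 1.96/√81 = 0.22 SD, but there is nothing to compare it with.

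**2. What a two-arm comparison would give**

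Inputs: 162 participants, 54 per risk group, 20% attrition over 3 months (SAP). Assumed: 1:1 allocation, and a correlation r between baseline and later self-blame of 0 (unadjusted), 0.5 or 0.7.

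Numbers per arm: 81 immediately; 162 × 0.8/2 = 64.8, about 65, at 3 months. Within one risk group: 54/2 = 27 and 54 × 0.8/2 = 21.6.

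Half-width of the 95% CI for the difference, in SD units = 1.96 × √((1 − r²) × 2/n).

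| | n per arm | r = 0 | r = 0.5 | r = 0.7 |
|---|---|---|---|---|
| Immediate | 81 | 0.31 | 0.27 | 0.22 |
| 3 months | 65 | 0.34 | 0.30 | 0.25 |
| One risk group, immediate | 27 | 0.53 | – | – |
| One risk group, 3 months | 21.6 | 0.60 | – | – |

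To show what this precision means, take a worsening of 0.5 SD. This is an illustration, not a proposed margin. If ASAP truly has no effect, the chance that the upper 95% limit falls below 0.5 SD is Φ(0.5/SE − 1.96), with SE = √((1 − r²) × 2/n).

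- Immediate, n = 81: 89% (r = 0), 96% (r = 0.5), 99% (r = 0.7).
- 3 months, n = 65: 81%, 91%, 98%.
- One risk group, unadjusted: 45% immediately, 38% at 3 months.

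These figures assume that everyone can answer the items. If only 60% to 40% could (assumed; the documents do not say so), the unadjusted half-widths would be 0.40 to 0.49 SD immediately and 0.44 to 0.54 SD at 3 months.

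**The case against.** **The instruments are unseen.** The protocol describes the baseline survey by topic, so its silence on self-blame is weak evidence. If the items are there, a pre-post change in the ASAP arm and a 3-month comparison between arms already exist. This stands, and it is why confirmation comes before any change. Even so, no analysis is named, the immediate check still lacks a comparator, and the claim in section 4.0 is still too strong.

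**Controls may take the post-intervention survey.** Section 10.0 gives out resources once that survey is completed and then says "All participants will be given this information, regardless of their risk". Section 3.0 is also loose: read literally, it would deny controls the 3-month survey that section 12.0 plainly gives them. So a reader should not infer that controls are certainly never asked. The one-arm reading is the more probable one, because the survey is introduced as the step after the intervention and no control survey is described at that point.

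**It is a pilot, and the stated purpose may mean only monitoring.** This is fair, and nothing here asks for a powered safety test. But a monitoring purpose still needs a stated summary and a conclusion that matches it.

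**Other protections exist.** A reader might infer that the trial has no means of seeing harm. The documents do not support that. The 3-month outcomes in both arms could show harm, a monitoring plan is to follow by amendment and could specify harm assessment (section 13.0), and suicidality assessment and access to a psychologist are planned (section 15.0). The point concerns only what the self-blame score can support.

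**Conclusion.** The point holds for the plan as described. Self-blame directly after the intervention is a one-arm score with no documented baseline score, no randomised comparator and no named analysis, so it cannot support the conclusion that section 4.0 attaches to it. Confidence is moderate because the survey instruments and the monitoring plan are not available.

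Two stronger readings should be resisted. Nothing in the documents suggests that ASAP raises self-blame; the gap is in the evidence. Nor is the pilot too small to say anything about moderate harm. With both arms measured, baseline adjustment at r = 0.5 to 0.7 and everyone answering, a 0.5 SD worsening would be excluded with about 91% to 98% probability at 3 months if there is truly no effect. The estimate would be useful for the whole sample and imprecise within one risk group (half-width about 0.53 to 0.60 SD unadjusted). The sizes rest on assumed 1:1 allocation and assumed correlations. The conclusion about the one-arm score does not depend on them.

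**What to change.** Before changing anything, confirm whether self-blame is in the Aim 3 baseline survey and whether controls answer any items after randomisation. Then:

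1. If the items are absent, add them to the baseline survey in both arms. They then repeat at 3 months.
2. Give controls the same items directly after randomisation, so that the immediate check has a randomised comparator. Record that their gap since baseline is shorter than in the ASAP arm, where the intervention of about 15 minutes comes between. A 3-month comparison alone would not do this job, because a brief rise could have passed by then.
3. Add to the SAP the ASAP-minus-control difference in self-blame, immediately and at 3 months, adjusted for baseline self-blame and risk group, with a 95% CI. State whom the items apply to. Show risk-group estimates descriptively only.
4. Reword section 4.0 so that the conclusion goes no further than the interval. If controls are not given the items, call the immediate score descriptive.

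**Cost.** If the items are already at baseline, steps 1 and 3 need only SAP text and a simple adjusted model at each time point, and step 2 adds a few items for controls. If not, up to 162 participants answer a few more sensitive online items at baseline and at 3 months. Asking about self-blame before ASAP may prime later answers, and the unequal gap at the immediate assessment cannot be fully removed. If no items are added, step 4 alone removes the over-claim but leaves no randomised estimate of the immediate effect.
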